8.2. Events or outcomes not qualifying as adverse events or serious adverse events

8.2.1. Pregnancy

Female subjects who are pregnant or lactating at the time of vaccination must not receive additional doses of study vaccine but may continue other study procedures at the discretion of the investigator.

While pregnancy itself is not considered an AE or SAE, any adverse pregnancy outcome or complication or elective termination of a pregnancy for medical reasons will be recorded and reported as an AE or a SAE.

Note: The pregnancy itself should always be recorded on an electronic pregnancy report.

The following should always be considered as SAE and will be reported as described in Sections 8.4.1 and 8.4.3:

- Spontaneous pregnancy loss, including:
 - spontaneous abortion, (spontaneous pregnancy loss before/at 22 weeks of gestation)
 - ectopic and molar pregnancy
 - stillbirth (intrauterine death of foetus after 22 weeks of gestation).

Note: the 22 weeks cut-off in gestational age is based on WHO-ICD 10 noted in the European Medicines Agency (EMA) Guideline on pregnancy exposure [EMA, 2006]. It is recognized that national regulations might be different.

- Any early neonatal death (i.e. death of a live born infant occurring within the first 7 days of life).
- Any congenital anomaly or birth defect (as per [Centers for Disease Control Metropolitan Atlanta Congenital Defects Program [CDC MACDP](#), 2007] guidelines) identified in the offspring of a study subject (either during pregnancy, at birth or later) regardless of whether the foetus is delivered dead or alive. This includes anomalies identified by prenatal ultrasound, amniocentesis or examination of the products of conception after elective or spontaneous abortion.

Furthermore, any SAE occurring as a result of a post-study pregnancy AND considered by the investigator to be reasonably related to the investigational vaccine will be reported to GSK Biologicals as described in Section 8.4.3. While the investigator is not obligated to actively seek this information from former study participants, he/she may learn of a pregnancy through spontaneous reporting.

8.3. Detecting and recording adverse events, serious adverse events and pregnancies

8.3.1. Time period for detecting and recording adverse events, serious adverse events and pregnancies

All AEs starting 30 days following administration of each dose of study vaccine (Day 0 to Day 29) must be recorded into the appropriate section of the eCRF, irrespective of intensity or whether or not they are considered vaccination-related.

The time period for collecting and recording SAEs will begin at the first receipt of study vaccine and will end 12 months following administration of the last dose of study vaccine for each subject. See Section 8.4 for instructions on reporting of SAEs.

The occurrence of suspected HZ will constitute an AE or SAE, as appropriate (and shall be reported in the HZ section of the eCRF [if an AE] or in the SAE and HZ section of the eCRF [if an SAE]). During the study, the time period for collecting and recording of suspected HZ will range from first receipt of study vaccine to study end. When a suspected HZ episode has been reported, specific clinical information about the case, following the first vaccination visit (Month 0) until study end (Month 14), will be entered into the eCRF. Please refer to the SPM for information about recording the details of suspected HZ cases.

All AEs/SAEs leading to withdrawal from the study will be collected and recorded from the time of the first receipt of study vaccine.

In addition to the above-mentioned reporting requirements and in order to fulfil international reporting obligations, SAEs that are related to study participation (i.e. protocol-mandated procedures, invasive tests, a change from existing therapy) or are related to a concurrent GSK medication/vaccine will be collected and recorded from the time the subject consents to participate in the study until she/he is discharged from the study.

The time period for collecting and recording pregnancies will begin at the first receipt of study vaccine and will end 12 Months following administration of the last dose of study vaccine. See Section 8.4 for instructions on reporting of pregnancies.

The time period for collecting and recording of pIMDs will begin at the first receipt of study vaccine and will end 12 Months following administration of the last dose of study vaccine. See Section 8.4 for instructions on reporting of pIMDs.

An overview of the protocol-required reporting periods for AEs, SAEs, and pregnancies is given in Table 10 (see also reporting methods below).

Table 10 Reporting periods for collecting safety information

Study activity	Pre-Vacc 1*	Visit 1 (Vacc 1)		Visit 2 (Vacc 2)		Visit 3/Month 3 phone contact (Post-vacc 2)	Month 8 phone contact SFU	Month 14# phone contact SFU
Time of reporting		Day 0/Month 0	Day 29 post Dose 1	Day 0/Month 2	Day 29 post Dose 2	Month 3	Month 8	Month 14#
Reporting of unsolicited AEs ¹								
Reporting of suspected HZ ²								
Reporting of AEs/SAEs leading to withdrawal from the study								
Reporting of all SAEs ²								
Reporting of SAEs related to study participation or GSK concomitant medication/vaccine								
Reporting of pregnancies								
Reporting of pIMDs								

AE: Adverse Event; SAE: Serious Adverse Event; pIMD: potential Immune-Mediated Disease; Vacc: Vaccination; M: Month

* i.e. consent obtained;

i.e. 12 months post dose 2

¹ Unsolicited AEs will be recorded in 30 day diary card

² At pre-vaccination, suspected HZ episodes will be collected as medical history (see section 5.6.4.). Post vaccination, suspected HZ will be recorded in the diary card as an AE/SAE within the Day 0 –Day 29 period and will also be reported during the Month 3, 8 and 14 contacts.

Type	Unsolicited adverse events/ SAEs, SAEs related to study participation or to GSK concomitant medication/vaccine; AEs/SAEs leading to withdrawal from the study.
Method of 'unsolicited' follow-up including suspected HZ	Diary cards
Method for reporting SAEs, SAEs related to study participation or to GSK concomitant medication/vaccine, Serious suspected HZ cases and pIMDs,	Electronic Expedited Adverse Events Report.
Suspected HZ cases (non-serious or serious)	HZ (if an AE)/HZ and SAE (if an SAE) screen of the eCRF
AEs/SAEs leading to withdrawal from the study	AEs/SAE screen of the eCRF

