In order to facilitate the documentation of pIMDs in the eCRF, a pIMD standard questionnaire and a list of Preferred Terms (PTs) and PT codes corresponding to the above diagnoses will be available to investigators at study start.

Once a pIMD is diagnosed (serious or non-serious) in a study subject, the investigator (or designate) must complete, date and sign an electronic Expedited Adverse Events Report.

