8.5.1.2. Follow-up after the subject is discharged from the study

The investigator will follow subjects:

- with SAEs, pIMDs (serious or non-serious), or subjects withdrawn from the study as a result of an AE, until the event has resolved, subsided, stabilised, disappeared, or until the event is otherwise explained, or the subject is lost to follow-up.
- with other non-serious AEs until 30 days after the last vaccination or they are lost to follow-up.

If the investigator receives additional relevant information on a previously reported SAE, he/she will provide this information to GSK Biologicals using an electronic Expedited Adverse Events Report and/or pregnancy report as applicable.

GSK Biologicals may request that the investigator performs or arranges the conduct of additional clinical examinations/tests and/or evaluations to elucidate as fully as possible the nature and/or causality of the AE or SAE. The investigator is obliged to assist. If a subject dies during participation in the study or during a recognised follow-up period, GSK Biologicals will be provided with any available post-mortem findings, including histopathology.

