9.2.2. Subject withdrawal from investigational vaccine

A 'withdrawal' from the investigational vaccine refers to any subject who does not receive the complete treatment, i.e. when no further planned dose is administered from the date of withdrawal. A subject withdrawn from the investigational vaccine may not necessarily be withdrawn from the study as further study procedures or follow-up may be performed (safety or immunogenicity) if planned in the study protocol.

All data collected until the date of withdrawal/last contact of the subject will be used for the analysis.

Information relative to premature discontinuation of the investigational vaccine will be documented on the Vaccine Administration screen of the eCRF. The investigator will document whether the decision to discontinue further vaccination was made by the subject himself/herself by the subject's LAR(s), or by the investigator, as well as which of the following possible reasons was responsible for withdrawal:

- Serious adverse event.
- Non-serious adverse event.
- Other (specify).

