Template 31 Listing of all SAEs from first vaccination until study end - by age sub-group (Total Vaccinated Cohort)

Goup	Sub-group*	Sub.No	Age at onset (Year)	Sex	Verbatim	Preferred term	System Organ Class	ME D type	Dose	Day of onset	Duration	Intensity	Causality	Outcome
[HZ/su]	[each age sub-group]													

*Age sub-group is based on subject's age at first vaccination
 50-59YOA = Subjects aged 50-59 years
 60-69YOA = Subjects aged 60-69 years
 70-79YOA = Subjects aged 70-79 years
 ≥80YOA = Subjects aged 80 years and over
 HZ/su = Herpes Zoster subunit vaccine group
 MED = Medically attended visit
 HO = Hospitalization,
 MD = medical personnel
 Please note this listing will also include the SAE related to only adjuvants which subject has received

Template 32 Listing of potential immune-mediated diseases (pIMDs) reported as identified by predefined list of preferred terms and/or by investigator assessment from first vaccination until study end - by age sub-group (Total Vaccinated Cohort)

Group	Sub-group	Patient ID	Country	Age at onset (Y)	Gender	Race	Primary System Organ Class	Preferred term
HZ/su	[each age sub-group]							

Group	Sub-group*	Dose	Day of onset	Relation	Serious pIMD based on Investigator?	SAE (Y/N)	Outcome	pIMD Source
HZ/su	[each age sub-group]							

*Age sub-group is based on subject's age at first vaccination
 50-59YOA = Subjects aged 50-59 years
 60-69YOA = Subjects aged 60-69 years
 70-79YOA = Subjects aged 70-79 years
 ≥80YOA = Subjects aged 80 years and over
 HZ/su = Herpes Zoster subunit vaccine

Template 33 Listing of dropouts due to AEs and SAEs from first vaccination until study end - by age sub-group (Total Vaccinated Cohort)

Group	Sub-group*	Study-Subject No.	Country	Gender	Race	AE Description	SAE	Causality	Outcome	Type of discontinuation
HZ/su	[each age sub-group]									

*Age sub-group is based on subject's age at first vaccination
 50-59YOA = Subjects aged 50-59 years
 60-69YOA = Subjects aged 60-69 years
 70-79YOA = Subjects aged 70-79 years
 ≥80YOA = Subjects aged 80 years and over
 HZ/su = Herpes Zoster subunit vaccine
 Type of discontinuation = discontinuation from study or from treatment

Template 34 Listing of subjects who died during the entire study period – by age group (Total Enrolled Cohort)

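### Protocol 8.3.1 and Table 10 require no AE record for some non-serious AEs that start from Day 30 and stop dose 2, yet SAP Template 33 expects their details

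*Protocol*

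**What the plan says.** Protocol 8.3.1 sets the general window: "All AEs starting 30 days following administration of each dose of study vaccine (Day 0 to Day 29) must be recorded". Outside it, the same section collects SAEs, suspected HZ and pIMDs for the whole study. On pIMDs it says: "The time period for collecting and recording of pIMDs will begin at the first receipt of study vaccine and will end 12 Months" after the last dose. Section 8.1.4.1 makes clear that non-serious pIMDs count ("Once a pIMD is diagnosed (serious or non-serious) in a study subject"). Section 5.4.1 sends non-serious suspected HZ outside the 30-day window to the HZ section of the eCRF.

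The remaining rule for AEs outside the window is: "All AEs/SAEs leading to withdrawal from the study will be collected and recorded from the time of the first receipt of study vaccine". Table 10 repeats the restriction in its row label, "Reporting of AEs/SAEs leading to withdrawal from the study". The matching row of Table 4 speaks of AEs that lead to withdrawal and does not say from what.

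Section 9.2 separates withdrawal from the study (9.2.1) from withdrawal from the vaccine (9.2.2). A subject may stop the vaccine and remain in the study. For that case: "Information relative to premature discontinuation of the investigational vaccine will be documented on the Vaccine Administration screen of the eCRF". The investigator records who decided and one of three reasons: SAE, non-serious AE, or other.

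SAP Template 33 lists dropouts due to AEs and SAEs from first vaccination to study end. Its columns include AE description, causality and outcome, and its footnote reads: "Type of discontinuation = discontinuation from study or from treatment". SAP Template 7 separately lists subjects withdrawn from vaccination, with dose, decision, reason and comment.

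**The concern.** The collection rule is tied to leaving the study, while the SAP listing covers leaving either the study or the treatment. The two coincide only if everyone who stops the vaccine because of an AE also leaves the study, and 9.2.2 says this need not be so.

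The protocol foresees such cases. Section 6.5 names grounds for withholding dose 2 that need not be SAEs, pIMDs or suspected HZ: an immunosuppressive condition, acute disease or fever, or a condition that makes the injection unsafe. For the absolute contraindications it allows the subject to continue other study procedures.

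Safety after each dose is the primary objective of this uncontrolled two-dose study, and AEs that stop the second dose bear on it directly. Protocol 10.7 and SAP 6.3.1 promise a detailed description of withdrawals due to AEs. If the AE record is optional for some of them, Template 33 will omit those subjects or show empty cells. Sites may also differ, depending on whether they work from Table 4 or from 8.3.1.

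**Working it through.** The plan gives no figure to reproduce on this point; Protocol 10.3 calculates no sample size. The check traces one case through the rules and then measures the window.

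**The case.** A subject receives dose 1 on Day 0. A non-serious AE starts on Day 30 or later but before Visit 2. Dose 2 is not given because of it, and the subject answers the Month 14 call.

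| Rule | Requires an AE record? |
|---|---|
| Days 0-29 after each dose (8.3.1) | No. Onset is too late after dose 1, and without dose 2 no second window opens |
| All SAEs; SAEs related to study participation or to a concurrent sponsor product (8.3.1) | No. The event is non-serious |
| pIMDs (8.1.4.1, 8.3.1) | Only if the event is a pIMD |
| Suspected HZ (5.4.1, 8.3.1) | Only if the event is suspected HZ |
| AE leading to study withdrawal (8.3.1, Table 10) | No. Under 9.2.1 a subject available for the concluding contact is not a withdrawal |
| AE leading to withdrawal (Table 4) | Unclear. The row does not say whether from study or vaccine |
| Vaccine Administration screen (9.2.2) | No. It holds decision maker and reason category only |

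If the event is neither a pIMD nor suspected HZ, no rule in 8.3.1 or Table 10 requires its term, onset, causality or outcome. Template 7 would show the subject with a reason and perhaps a comment. Template 33 has columns for description, causality and outcome but no collection rule that guarantees their content.

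**The window.** Table 5 allows Visit 2 from 49 to 83 days after Visit 1, with 60 as the optimum. Counting dose 1 as Day 0, the uncovered days run from Day 30 to the day before Visit 2:

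uncovered days = Visit 2 day − 30; share of interval = uncovered days / Visit 2 day

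| Visit 2 on | Uncovered days | Share of calendar days |
|---|---|---|
| Day 49 | 49 − 30 = 19 | 19/49 = 39% |
| Day 60 | 60 − 30 = 30 | 30/60 = 50% |
| Day 83 | 83 − 30 = 53 | 53/83 = 64% |

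**Follow-up of AEs that are recorded.** For a subject still in the study, 8.5.1.1 reviews unresolved AEs other than SAEs and pIMDs until 30 days after the last vaccination. After discharge, 8.5.1.2 sets the same limit: "with other non-serious AEs until 30 days after the last vaccination or they are lost to follow-up". If dose 1 was the last dose, that limit falls 19, 30 or 53 days before a Visit 2 on Day 49, 60 or 83. An AE that causes study withdrawal is instead followed under 8.5.1.2 until it resolves or stabilises.

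**The case against.** The strongest reply is that much of this is covered elsewhere.

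- A reader might infer that, after Day 29, non-serious AEs are kept only when the subject leaves the study. The documents do not support that. Non-serious pIMDs and non-serious suspected HZ are collected throughout, and both appear in 6.5 among the events that can stop further vaccination. The gap is confined to other non-serious AEs.
- A reader might infer that these discontinuations go unrecorded. They do not. Section 9.2.2 requires the discontinuation, the decision maker and the reason. Template 7 lists them, and SAP 6.1.2 and 6.3.2 both commit to that listing. What is missing is a required AE record.
- Table 4 can fairly be read to include vaccine withdrawal, because 9.2.2 itself calls stopping the vaccine a withdrawal. This stands as an ambiguity. It does not close the gap, since 8.3.1 and Table 10 use the narrower wording. The eCRF and the Study Procedures Manual, which might settle it, are not available here.
- Section 8.3.3.1 has subjects asked an open question about how they have felt, and an investigator may enter such an AE in practice. That helps detection but does not extend the reporting period.
- The follow-up point is weaker for AEs that start on Days 0-29. The dose 1 diary card is collected and transcribed at Visit 2, so term, causality and outcome are normally available when dose 2 is decided.
- Acute illness or fever allows rescheduling within the visit window, which removes some cases.

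**Conclusion.** The point stands in a limited form. Under 8.3.1 and Table 10, a non-serious AE that is neither a pIMD nor suspected HZ, starts between Day 30 after dose 1 and Visit 2, and stops dose 2 in a subject who stays in the study, needs no AE record. Template 33 expects one, so the listing may be incomplete for these subjects.

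The window is 19 to 53 days, depending on when Visit 2 falls. The shares of 39%, 50% and 64% are shares of calendar days. A reader might take them as the proportion of AE-related discontinuations lost; the documents give no basis for that. They contain no count of affected subjects and no rate from which to estimate one. The number is probably small, because SAEs, pIMDs, suspected HZ and rescheduled visits are all outside the gap.

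The conclusion assumes that sites follow 8.3.1 and Table 10 as written, and that no eCRF or manual instruction requires the fuller record. It is worth fixing because a primary-objective listing and the rule that feeds it disagree, and a few words reconcile them.

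**What to change.** In Protocol 8.3.1, Table 10 and Table 4, use one wording: AEs and SAEs that lead to withdrawal from the study or from further vaccination, collected from the first dose. This brings the three places into line with 9.2.2 and Template 33. Reconcile the follow-up limits in 8.5.1.1 and 8.5.1.2 with that wording, so that they state how an AE that ends vaccination is followed in a subject who stays in and in one who is discharged.

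In the SAP, Templates 17 and 24 already count subjects with one dose. Add the 9.2.2 reasons for dose 2 not given.

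The final SAP is dated 26 February 2019 and already cites subject counts by age group, so it may be too late to change collection. In that case, check Template 33 against Template 7, identify subjects whose vaccine was stopped for a non-serious AE without a matching AE entry, and footnote Template 33 with the collection limit.

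The cost is a few wording changes, one extra AE entry per affected subject, and any added follow-up that the reconciled limits bring. The Vaccine Administration screen already identifies who these subjects are.

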8.3.2. Post-Study adverse events and serious adverse events

A post-study AE/SAE is defined as any event that occurs outside of the AE/SAE reporting period defined in Table 10. Investigators are not obligated to actively seek AEs or SAEs in former study participants. However, if the investigator learns of any SAE at any time after a subject has been discharged from the study, and he/she considers the event reasonably related to the investigational vaccine, the investigator will promptly notify the Study Contact for Reporting SAEs.

8.3.3. Evaluation of adverse events and serious adverse events

8.3.3.1. Active questioning to detect adverse events and serious adverse events

As a consistent method of collecting AEs, the subject or the subject’s LAR(s) should be asked a non-leading question such as:

‘Have you felt different in any way since receiving the vaccine or since the previous visit?’

When an AE/SAE occurs, it is the responsibility of the investigator to review all documentation (e.g. hospital progress notes, laboratory and diagnostics reports) relative to the event. The investigator will then record all relevant information regarding an AE/SAE in the eCRF. The investigator is not allowed to send photocopies of the subject’s medical records to GSK Biologicals instead of appropriately completing the eCRF. However, there may be instances when copies of medical records for certain cases are requested by GSK Biologicals. In this instance, all subject identifiers will be blinded on the copies of the medical records prior to submission to GSK Biologicals.

The investigator will attempt to establish a diagnosis pertaining to the event based on signs, symptoms, and/or other clinical information. In such cases, the diagnosis should be documented as the AE/SAE and not the individual signs/symptoms.

8.3.3.2. Assessment of adverse events

8.3.3.2.1. Assessment of intensity

The investigator will assess the maximum intensity that occurred over the duration of the event for all unsolicited AEs (including SAEs) recorded during the study. The assessment will be based on the investigator's clinical judgement.

The intensity should be assigned to one of the following categories:

- 1 (mild) = An AE which is easily tolerated by the subject, causing minimal discomfort and not interfering with everyday activities.
- 2 (moderate) = An AE which is sufficiently discomforting to interfere with normal everyday activities.
- 3 (severe) = An AE which prevents normal, everyday activities. Such an AE would, for example prevent attendance at work and would necessitate the administration of corrective therapy.

An AE that is assessed as Grade 3 (severe) should not be confused with a SAE. Grade 3 is a category used for rating the intensity of an event; and both AEs and SAEs can be assessed as Grade 3. An event is defined as 'serious' when it meets one of the pre-defined outcomes as described in Section 8.1.2.

8.3.3.2.2. Assessment of causality

The investigator is obligated to assess the relationship between investigational vaccine and the occurrence of each AE/SAE. The investigator will use clinical judgement to determine the relationship. Alternative plausible causes, such as natural history of the underlying diseases, concomitant therapy, other risk factors, and the temporal relationship of the event to the investigational vaccine will be considered and investigated. The investigator will also consult the IB and/or summary of product characteristics to determine his/her assessment.

There may be situations when a SAE has occurred and the investigator has minimal information to include in the initial report to GSK Biologicals. However, it is very important that the investigator always makes an assessment of causality for every event prior to submission of the Expedited Adverse Events Report to GSK Biologicals. The investigator may change his/her opinion of causality in light of follow-up information and update the SAE information accordingly. The causality assessment is one of the criteria used when determining regulatory reporting requirements.

In case of concomitant administration of multiple vaccines/products, it may not be possible to determine the causal relationship of general AEs to the individual vaccine/product administered. The investigator should, therefore, assess whether the AE could be causally related to vaccination rather than to the individual vaccines.

Causality of all other AEs should be assessed by the investigator using the following question:

Is there a reasonable possibility that the AE may have been caused by the investigational vaccine?

- YES : There is a reasonable possibility that the vaccine contributed to the AE.
- NO : There is no reasonable possibility that the AE is causally related to the administration of the study vaccine. There are other, more likely causes and administration of the study vaccine is not suspected to have contributed to the AE.

If an event meets the criteria to be determined as ‘serious’ (see Section 8.1.2), additional examinations/tests will be performed by the investigator in order to determine ALL possible contributing factors for each SAE.

Possible contributing factors include:

- Medical history.
- Other medication.
- Protocol required procedure.
- Other procedure not required by the protocol.
- Lack of efficacy of the vaccine, if applicable.
- Erroneous administration.
- Other cause (specify).

